### Medical Therapy for Atrial Fibrillation:

Anti-arrhythmic drugs (AADs) choice will be based on the treating physicians' preference but will be in accordance with HRS, ACC, AHA, ESC guidelines.

### Detection of Atrial Fibrillation:

In the general population AF is usually detected during workup of palpitations or during routine physical exams/ECGs in patients with no symptoms of palpitations. Also it may be detected during workup of stroke or peripheral thromboembolism.

In the group intended for this study AF should be **symptomatic** for inclusion. However after treatment with PVI or AADs it is not unusual for patients to develop asymptomatic AF recurrence. As such implanted devices (already implanted for clinical indications) may be used to assess for recurrence of AF in conjunction with device and event monitoring.

CONFIDENTIAL

This document is confidential and the property of The Cleveland Clinic Foundation. No part of it may be transmitted, reproduced, published, or used by other persons without prior written authorization from the study sponsor.

V6.0\_22May2017

## 2 Study Objectives

### 2.1 Objectives

- To determine if catheter-based atrial fibrillation (AF) ablation is superior to medical treatment in patients with impaired left ventricular function that has been diagnosed with symptomatic AF within the past 12 months.
- Hypothesis: In patients with an early diagnosis of AF, ablation is better than medical therapy for patients with symptomatic AF and impaired LV function in terms of recurrent and total number of hospitalizations, recurrence of AF, EF, quality of life, and 6-minute walk distance.

## 3 Study Endpoints

Timeframe to endpoints: After the 3 month treatment period, the endpoints will be assessed for 12 months

### 3.1 Primary Endpoint

Time to first hospitalization (> 24 hours) for Heart Failure, recurrence of AF or DC cardioversion after the treatment period

### 3.2 Secondary Endpoints

- Total number of cardiovascular hospitalizations during the trial period for each group
- Time to Recurrence of AF lasting longer than 30 seconds
- Change in distance walked in 6-minute walk test
- Change in the Rand 36-Item Health Survey (SF-36) during trial period
- Change in EF during trial period

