## 5.2 Inclusion Criteria

---

Patients must meet all of the following criteria:

1. Be  $\geq 18$  years of age
2. Provide signed written Informed Consent
3. Symptomatic AF documented by ECG or heart rhythm monitoring within 12 months
4. Patients should be on optimal medical therapy for HF (heart failure) for 3 months prior to randomization. Adjustments to medications within this 3 month period are permitted.
5. Chronically impaired LV function defined as EF 20%-45% within the last 3 months by echocardiogram, nuclear imaging, MRI or cardiac catheterization
6. All patients should be on an optimal therapy for impaired LV function. Optimal therapy includes at least one ACE inhibitor or angiotensin receptor blockers (ARB) in ACE-intolerant patients along with beta blockers for at least 3 months. For those patients intolerant to ACE/ARB's, a combination of hydralazine and isosorbide dinitrate is recommended. NYHA class III patients may be prescribed spironolactone
7. Ability to complete 6 minute walk test
8. Be eligible for catheter ablation and anti-arrhythmic drugs

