### 6.4.2 12-15 Month Post Randomization Visit (+/- 3 weeks)

1. Record data from office visit if completed as standard of care
2. Record vital signs (HR/BP)
3. Record use of select medications
4. Record 12 lead ECG
5. Record Echocardiogram
6. Perform 6-minute walk test
7. Collect Rand 36-Item Health Survey (SF-36)
8. Collect Atrial Fibrillation severity Scale (AFSS)
9. Assessment of NYHA class
10. Record the data from remote arrhythmia monitoring and /or ECGs completed as a part of standard of care
11. Record the results from routine lab assessment and clinical indicated tests completed as a part of Standard of care: these may include but not limited to:
  - Blood tests, chest x-rays, pulmonary function test, Spiral CT to assess pulmonary vein stenosis (only if in the ablation arm only if clinically indicated )
12. Assessment of Adverse Events (AE) and Serious Adverse Events (SAE)
13. Record any hospitalizations including short stays and hospital admissions.

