## 7 Statistical Analysis

A Cox proportional hazards regression model adjusting for site and randomization strata will be used to test for treatment group differences in the primary endpoint. Kaplan-Meier estimates and curves will also be created. Secondary endpoints will be analyzed using a two-sample t-test or Wilcoxon signed rank as appropriate. Depending on the distribution for the total number of hospitalizations it will be treated as a continuous variable or collapsed into categories (0-2, 3-5, 5-7, >7). The intent-to-treat population will be used for all analysis. Patients who drop-out before study completion due to cardiac causes will be considered as having an event at the time drop-out for the primary analysis. Patients who drop-out for other reasons will be treated as censored observations at the time of drop-out in the primary analysis. Analysis based on the protocol and safety populations will also be done. All statistical tests will be two-sided and an alpha of 0.05 or less will be considered statistically significant. Mean and

CONFIDENTIAL

This document is confidential and the property of The Cleveland Clinic Foundation. No part of it may be transmitted, reproduced, published, or used by other persons without prior written authorization from the study sponsor.

V6.0\_22May2017

standard deviation or frequency and percent will be used to describe demographics, medical history and other baseline variables by treatment group. T-tests or chi-square tests as appropriate will be used to compare the baseline factors by treatment group.

Sample size is based on an expected 30-40% rate of hospitalization for recurrence of AF, heart failure or DC conversion at 12 months in the ablation arm and a 60% rate at 12 months in the AAD arm. One hundred patients per treatment arm are needed to have 80% power at an alpha level of 0.05 to detect this difference. Assuming a 10% drop-out rate, a total of 220 patients will need to be enrolled. Randomization will be 1:1 based on EF stratification EF  $\leq$ 35% and >35%.

**Safety population:** All patients that received any ablation treatment **or at least 1 dose of AAD** will be included in the safety population.

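### The 6-minute walk endpoint has no value for patients who die or cannot walk at follow-up, and the rank test named for it is a paired test that does not compare the arms

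*Combined protocol and SAP*

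**What the plan says.** The endpoint is given in one line, "Change in distance walked in 6-minute walk test" (Section 3.2), and walk distance is named in the hypothesis in Section 2.1. The line states no time point. The walk is done at baseline (Section 6.3) and at the 3-6 and 12-15 month visits (Sections 6.4.1 and 6.4.2). The instruction at follow-up is only "Perform 6-minute walk test", with nothing on what to record if the patient cannot do it. Entry requires "Ability to complete 6 minute walk test" and "Chronically impaired LV function defined as EF 20%-45% within the last 3 months" (Section 5.2).

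On analysis, Section 7 says "Secondary endpoints will be analyzed using a two-sample t-test or Wilcoxon signed rank as appropriate" and "The intent-to-treat population will be used for all analysis". Its two rules for drop-outs are "Patients who drop-out before study completion due to cardiac causes will be considered as having an event at the time drop-out for the primary analysis" and "Patients who drop-out for other reasons will be treated as censored observations at the time of drop-out in the primary analysis". Both end by limiting themselves to the primary analysis. No section gives a value, rank, imputation or sensitivity analysis for a missing follow-up walk.

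**The concern.** Every patient can complete the walk at entry, so losing that ability through illness, or dying, is an outcome that arises during the trial and lies at the bad end of the scale the endpoint is meant to measure. A change score needs a follow-up distance. Without one the patient cannot enter a t-test or a rank test on change, and the intention-to-treat sentence does not alter that: it says who belongs to the analysis set, not what value they receive.

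At stake is one of the outcomes on which the trial claims that ablation is better. If one arm loses more patients to death or decline, the comparison among remaining walkers favours that arm. Because the arms are open (Section 4), a rule chosen after the data are seen would carry little weight.

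A second fault sits in the same sentence of Section 7. The Wilcoxon signed rank test is for paired data. Applied to changes within one arm, it asks whether that arm's change is centred on zero. It does not test ablation against drug therapy.

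**Working it through.** **1. Is there a rule anywhere?** Section 3.2 gives the endpoint without a rule. Section 5.2 requires walking ability at entry only. Sections 6.4.1 and 6.4.2 ask for the test with no alternative. Section 7 has drop-out rules for the primary analysis only, and the population definitions in Section 7.1 say nothing on missing values. So no rule exists, and omission is what follows if the named tests are run on the available changes.

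**2. The plan's own figures.** The plan gives no power, SD or expected difference for the walk. Its sample size belongs to the primary endpoint and reproduces at the 40% end of its range: n = [1.96√(2×0.5×0.5) + 0.842√(0.4×0.6 + 0.6×0.4)]² / 0.2² = 1.969²/0.04 ≈ 97 per arm, against 100 stated. Power with 100 per arm is 81.2%. Drop-out: 200/0.9 = 223, against 220. I take only the 100 per arm from this.

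**3. Illustrative size.** Assumptions, none of them in the documents: SD of change 80 m; true difference 30 m in favour of ablation; losses (death or inability) of 3-5% in the ablation arm and 3-20% in the drug arm; correlation 0.5 between the tendency to be lost and a worse change. Removing a share p of patients in this way raises the mean of those left by 0.5 × 80 × φ(z_p)/(1−p), where z_p is the normal quantile at p and φ the normal density:

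- p = 3%: 40 × 0.0680/0.97 = 2.8 m
- p = 5%: 40 × 0.1031/0.95 = 4.3 m
- p = 6%: 40 × 0.1191/0.94 = 5.1 m
- p = 10%: 40 × 0.1755/0.90 = 7.8 m
- p = 20%: 40 × 0.2800/0.80 = 14.0 m

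The expected observed difference is 30 minus the gap between the two arms. Power is by simulation with 100 per arm (2,000 or more runs per scenario, so good to about 1-2 percentage points). Worst-rank means a rank-sum test with every lost patient ranked lowest.

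| Losses, ablation v drug | Expected observed difference | Power, t-test on observed changes | Power, worst-rank |
|---|---|---|---|
| 5% v 5% | 30 − 0 = 30 m | 75-77% | 66-67% |
| 3% v 6% | 30 − (5.1 − 2.8) ≈ 28 m | 68-69% | 74% |
| 3% v 10% | 30 − (7.8 − 2.8) = 25 m | about 60% | 80-82% |
| 5% v 20% | 30 − (14.0 − 4.3) ≈ 20 m | 41-42% | 90-91% |

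**4. No difference among walkers, losses unrelated to change.** With 5% lost on ablation and 10%, 15% or 20% on drugs, the t-test on observed changes was significant in 5.2%, 4.5% and 4.8% of runs, which is the false-positive level. Worst-rank was significant in 10.9%, 24.4% and 46.2%. The observed-only test is blind to a difference that consists only of deaths and inability.

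**The case against.** The plan does not say that these patients are excluded. It is silent, and the same silence covers change in SF-36 and in EF. That is right: exclusion is an inference from the named tests, and the gap is a general one. It is sharpest for the walk, where inability to do the test is itself a result.

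Serious decline would also show elsewhere. Heart failure hospitalisation is in the primary endpoint, cardiac drop-out counts as a primary event, NYHA class is assessed at both follow-up visits, and fatal events are serious adverse events. So a reader should not infer that such patients go unrecorded. None of this repairs the walk comparison.

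Change among survivors, with deaths reported beside it, is a defensible alternative target. It would have to be chosen and stated in advance, and it is not.

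Three stronger readings are tempting, and the documents support none of them:

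- *That omission reverses the true difference.* With a true 30 m difference, the most unequal case examined (5% v 20%) still left about 20 m in the same direction.
- *That the test hides 9-28 m.* Scoring lost patients as 0 m would move a mean difference by (0.06 − 0.03) × 300 = 9 m to (0.10 − 0.03) × 400 = 28 m, taking walkers' mean change as near zero. The baseline distances and rates are assumed. The result is the shift in a composite score, not the bias in the planned test, which at the same loss rates is about 2-5 m.
- *That the drug arm will lose more patients.* Section 1.1 cites a 47% lower risk of death with sinus rhythm and a 49% higher mortality with antiarrhythmic drugs. These are associations from another study and give no loss rate for this trial. If ablation lost more, the bias would run the other way.

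**Conclusion.** The point holds as a gap with a conditional effect. Run on observed changes, the walk comparison covers only surviving walkers, and it can understate or mask a functional difference if death or inability differs between arms. With equal losses no bias in the difference is expected. At 3% v 6% and 3% v 10% losses, the illustration loses about 2-5 m of a true 30 m, and power falls from about 75-77% (equal losses) to about 68% and 60%. The larger effects need 15-20% losses in one arm; with 5% in the other, that averages 10-12.5% overall, at or above the plan's whole 10% drop-out allowance. All of these sizes rest on the assumed SD, difference, loss rates and correlation.

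The fault in the named rank test needs no assumption: a signed rank test does not compare two independent arms.

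This is a secondary endpoint and no sample size depends on it. It should be corrected before analysis, but it does not threaten the primary result.

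**What to change.** - In Section 7, replace the signed rank test with the Wilcoxon rank-sum (Mann-Whitney) test for between-arm comparisons.
- In Section 3.2, define the endpoint as change from baseline to the 12-15 month visit.
- Assign death the lowest rank and inability to walk because of illness the next lowest. Use ranks, not 0 m: on a change scale 0 m becomes minus the baseline distance, so a patient who can no longer walk from a 200 m baseline (−200 m) would rank above a walker who lost 250 m.
- State a missing-data method for all other missing walks (refused, missed visit, other reasons).
- Report alongside it the observed-case mean difference in metres, and deaths and inability by arm.
- Add a CRF field for the reason a walk was not done, with set categories, completed at the visit.
- Because the trial is unblinded, add a sensitivity analysis that ranks all illness-related inability as worst, whatever cause was attributed.

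The cost is endpoint and analysis wording and one CRF field; there is no new procedure. The rank result is harder to read in metres, which is why the observed mean stays. It also loses some power if losses turn out equal (about 66-67% against 75-77% in the 5% v 5% illustration).

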## Study Synopsis

Title	Catheter Ablation vs. Medical Therapy in Congested Hearts with AF (CATCH-AF in Patients with impaired LV function)
Protocol Number	6.0
Study Treatment	Strategy of Early Atrial Fibrillation Ablation compared to conventional Anti-Arrhythmic Drug management.
Indication	Chronically impaired LV function on optimal medical therapy with first encounter for new symptomatic AF diagnosis within 12 months.
Study Design	This study is a, multi-center, randomized, unblinded, clinical trial with the objective of enrolling 220 patients over approximately 18 months.
Study Objectives	
 
• To determine if catheter-based atrial fibrillation (AF) ablation is superior to medical treatment in patients with impaired left ventricular function who have been diagnosed with symptomatic AF within the past 12 months
 
• Hypothesis: AF ablation is better than medical therapy for patients with symptomatic AF and impaired LV function in terms of recurrent and total number of hospitalizations, recurrence of AF, EF, quality of life, and 6-minute walk distance.
 

Primary Endpoint	The primary endpoint is time to first hospitalization (>24hr) for heart failure, recurrence of AF or DC cardioversion after the treatment period
Secondary Endpoint	Secondary endpoints will include evaluation of the following: 
 
• Total number of cardiovascular hospitalizations during the trial period for each group
 
• Time to Recurrence of AF lasting longer than 30 seconds
 
• Change in distance walked in 6-minute walk test
 
• Change in Rand 36-Item Health Survey (SF-36) during trial period
 
• Change in EF during trial period
 

Duration of Treatment and Study Period	The time course for the trial is divided into a treatment period followed by the trial period. The treatment period will include the first 3 months post enrollment. The trial period will commence at end of treatment period and all outcome data will be collected over a 12 month period.

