## Study Assessments:

Procedure	Screening/ Baseline/ Randomization Visit	3-6 month Follow-up Visit (+/- 3 weeks)	12-15 month Follow-up Visit (+/- 3 weeks)
Confirm Inclusion/Exclusion Criteria	X		
Obtain Informed Consent	X		
Verify that females are not of childbearing potential 	X		
Randomization	X		
Record Medical History and Physical	X		
Record Vital Signs HR/BP	X	X	X
Record Medications	X	X	X
Record ECG	X	X	X
Record Echocardiogram	X		X
6 minute walk test	X	X	X
Record Routine Lab Assessments	X	X	X
Record Clinically Indicated Tests	X	X	X
Rand 36-Item Health Survey (SF-36)	X	X	X
AFSS QOL	X	X	X
Assessment NYHA	X	X	X
Arrhythmia Monitoring	X	X	X
Assessment of SAE/AE		X	X
Assessment of Hospitalization		X	X

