**1. Verify that female subject is post-menopausal /surgically sterile following individual site standard of care process**

Note: Baseline assessments to be completed before assigned treatment initiated.

**If the above assessments are collected as part of routine care, please record the information on the Case Report Form (CRF) at the study visit time points. For the ablation arm, record date of ablation and target areas on the CRF.**

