## 6 Study Procedures

The time course for the trial is divided into a treatment period followed by the trial period. The treatment period will include the first 3 months post enrollment or post procedure during which repeat ablation can be performed and titration of AAD dosages can be performed. The follow-up trial period will commence at end of treatment period and all outcome data will be collected over a 12 month period.

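### SF-36 and EF change are tied to a trial period that begins after treatment, and walk-test change has no stated start: define all three from the pre-treatment baseline, replace the signed-rank test, and adjust for baseline and EF stratum

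*Combined protocol and SAP*

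**What the plan says.** Section 3.2 lists "Change in EF during trial period" and "Change in the Rand 36-Item Health Survey (SF-36) during trial period" as secondary endpoints. The walk-test endpoint reads only "Change in distance walked in 6-minute walk test". The Synopsis lists the same three.

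The trial period is a defined term. The Synopsis states: "The trial period will commence at end of treatment period and all outcome data will be collected over a 12 month period". Section 6 repeats this, and section 3 sets the time frame for all endpoints: "After the 3 month treatment period, the endpoints will be assessed for 12 months". The treatment period is the first three months after enrollment; section 6 adds the alternative of three months after the procedure.

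In the Study Assessments table, the row "Record Echocardiogram" is marked at baseline and at the 12-15 month visit and is blank at the 3-6 month visit. Sections 6.3, 6.4.1 and 6.4.2 agree. SF-36 and the walk test are marked at all three visits. A note under the table says "Baseline assessments to be completed before assigned treatment initiated". No sentence names that baseline value as the start of any change.

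Section 7 compares secondary endpoints by a two-sample t-test or the Wilcoxon signed-rank test. Adjustment for site and randomization strata is stated only for the primary Cox model. Section 5.4 stratifies randomization by EF at 35%.

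**The concern.** A change endpoint needs a stated first value and a stated last value. Here the defined period puts the first value after treatment has begun, while the schedule collects a pre-treatment value that no definition uses. For SF-36 and the walk test, two possible starting values will be in the database of an unblinded trial, and the choice could be made after results are known. The choice also alters the effect being estimated: starting at the 3-6 month visit leaves out whatever the treatments have already achieved.

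The named non-parametric test is a separate fault. The signed-rank test examines paired differences within one group and does not compare two independent arms. Finally, the analysis of change leaves unused, as covariates, a baseline value already collected and the EF stratum on which randomization was balanced. These endpoints matter because EF, quality of life and walk distance are all named in the study hypothesis (section 2.1).

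**Working it through.** **Inputs.** From the documents: visit windows of plus or minus 3 weeks (21/30.4 = 0.69 month), 100 patients per arm, and a trial period from month 3 to month 15, with the clock taken to start at randomization. Assumed, because the documents give no SD or correlation: k = baseline SD / follow-up SD, and rho = correlation between baseline and follow-up.

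**1. The plan's own figure.** The only sample size given is for the primary endpoint. For 40% against 60%, two-sided 0.05 and 80% power, the two-proportion formula gives [1.96 × √(2 × 0.5 × 0.5) + 0.842 × √(0.4 × 0.6 + 0.6 × 0.4)]² / 0.2² = 97 per arm. The stated 100 per arm gives 81.2% power, and 200 × 1.10 = 220. The figure reproduces, and nothing in it depends on EF, SF-36 or walk distance.

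**2. Scheduled values.**

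| Measure | Before treatment | 3-6 months | 12-15 months |
|---|---|---|---|
| EF (echocardiogram) | yes | no | yes |
| SF-36 | yes | yes | yes |
| Walk test | yes | yes | yes |

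EF has no scheduled value near the start of the trial period, so only baseline to 12-15 months can be computed. SF-36 and the walk test have two candidate starts.

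**3. Timing under the literal SF-36 reading.**
- The 3-6 month visit can fall from 3 − 0.69 = 2.3 to 6 + 0.69 = 6.7 months, so it may precede the trial period.
- The 12-15 month visit can fall from 12 − 0.69 = 11.3 to 15 + 0.69 = 15.7 months.
- The shortest interval between visits is 11.3 − 6.7 = 4.6 months. With both values inside months 3 to 15, the longest is 15 − 3 = 12 months.

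**4. What the literal reading could cost (illustration only).** Assume a true effect of 0.4 SD, equal SDs, a correlation of 0.5 and 100 per arm. If a fraction f of the effect is present by the 3-6 month visit, power is Φ(0.4(1 − f) / √(2/100) − 1.96). That is 81% at f = 0, 56% at 0.25, 29% at 0.5 and 11% at 0.75. The documents give neither the effect size nor f.

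**5. ANCOVA against the t-test on change, large samples, no stratified balance.** With s the follow-up SD, Var(change) = s²(1 + k² − 2·rho·k) and Var(ANCOVA) = s²(1 − rho²). The difference is s²(k − rho)², which is zero at k = rho and never negative. Variance ratios, ANCOVA to change:

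| k | rho 0.3 | rho 0.6 | rho 0.8 |
|---|---|---|---|
| 1 | 0.65 | 0.80 | 0.90 |
| 0.85 | 0.75 | 0.91 | 0.99 |
| 0.7 | 0.85 | 0.98 | 0.97 |

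Example: k = 1, rho = 0.3 gives 0.91/1.40 = 0.65. The saving over this grid is about 1% to 35%.

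**6. EF, allowing for stratified randomization.** The simulation used n = 200, 20,000 runs, normal data, 1:1 allocation within two strata split at the median baseline, and no treatment effect. Each cell shows the variance ratio, then the type I error of the t-test on change:

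| k | rho 0.3 | rho 0.6 | rho 0.8 |
|---|---|---|---|
| 1 | 0.84; 2.75% | 0.92; 3.65% | 0.97; 4.15% |
| 0.85 | 0.89; 3.28% | 0.97; 4.25% | 1.00; 4.61% |
| 0.7 | 0.95; 3.88% | 1.00; 4.86% | 0.99; 4.74% |

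ANCOVA type I error was 4.7% to 5.0% throughout. With strata split about 24:76, the ratio at k = 1, rho = 0.3 was 0.80 instead of 0.84.

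**7. Worst-case loss.** With two covariates and n = 200, the finite-sample variance factor is 1 + 2/195 = 1.010, about 1%.

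**The case against.** The strongest reply is that the intent is plain. Section 3 says when endpoints are assessed, so the phrase about the trial period may fix when the outcome value is taken and not where change begins. All three measures are collected before treatment, and EF and SF-36 share the same wording. If EF can only mean change from baseline, SF-36 should mean the same. On analysis, a t-test on change is valid under randomization, and every precision figure rests on assumed inputs.

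Much of this stands. Change from baseline is a fair reading, and for EF the only workable one. But the defined term says otherwise, no sentence names baseline as the reference, and for SF-36 the literal reading can be carried out. The schedule therefore does not settle the matter. The validity of the t-test is accepted, but that does not rescue the signed-rank test.

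A reader might go further than the documents allow:
- *That EF change cannot be analysed at all.* Both scheduled echocardiograms are usable; the wording is wrong, not the data collection.
- *That the plan will discard early SF-36 benefit.* This follows only from the literal reading, and the power losses in step 4 rest on assumptions.
- *That SF-36 change could span 13.4 months.* The outer visit windows give 15.7 − 2.3 = 13.4, but change within a 12-month trial period cannot be that long.
- *That the t-test ignores baseline or is biased.* A change score subtracts baseline; what is missing is adjustment for it as a covariate.
- *That adjustment would save 35% for EF.* That figure ignores the stratified balance and takes k = 1. Inclusion criterion 5 restricts baseline EF to 20-45%, so k below 1 is plausible, and at k = 0.7 the simulated saving is 0-5%.
- *That echocardiograms are optional because sites are told to record and not to perform them.* Vital signs and ECG are worded the same way.

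**Conclusion.** The point holds as one of definition and analysis for secondary endpoints. It should be corrected before the data are examined. In order of weight:

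- **Start of change.** It is open for SF-36 and the walk test. Under the literal reading, SF-36 change would start after treatment began and run over about 4.6 to 12 months. The benefit left out is of unknown size. For EF this is a wording correction only.
- **Wrong test.** The signed-rank test cannot make the between-arm comparison that section 7 assigns to it. This needs no assumption.
- **Adjustment.** ANCOVA is a modest improvement, not the repair of an invalid method. The variance saving is about 1-35% in large samples without stratified balance, and zero when k equals rho. For EF it is about 0-16% in simulation with equal strata. The unadjusted EF test is valid but somewhat conservative, at about 3-5% type I error. These figures depend on the assumed k and rho, and the simulation used normal data without truncating baseline EF.

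The primary endpoint analysis and the total of 220 are unaffected.

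**What to change.** 1. In the Synopsis and section 3.2, define SF-36, walk distance and EF change as the value at the 12-15 month visit minus the pre-treatment baseline value.
2. In section 7, replace the Wilcoxon signed-rank test with the Wilcoxon rank-sum test.
3. In section 7, analyse each of the three endpoints by ANCOVA with treatment, baseline value and EF stratum, and keep the unadjusted two-sample test as supportive. For EF, continuous baseline EF and the stratum can both be in the model, since the stratum is only a coarse form of the same measurement.

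The cost is a change of wording and a little more analysis work, with a worst-case precision loss of about 1%. No visit, assessment or patient is added.
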